Short Title	A Microdose Evaluation Study of ABY-029 in Recurrent Glioma
Protocol Number	N/A
Phase	Phase 0 microdose
Methodology	Patients will be administered a single intravenous dose of ABY-029 1-3 hours before surgery. At different times during resection, the coregistered surgical microscope (Zeiss Pentero enabled with intraoperative fluorescence imaging, iFI) will be focused on a point of interest. The surgeon will switch to iFI mode to capture images of the surgical field. Quantitative measurements of fluorophore concentration will be made at the focal point of the operating microscope with an intraoperative probe and biopsy samples will be taken at the coregistered point of interest for subsequent histological analyses and ex-vivo assessments of fluorophore concentration. In addition, an imaging array mounted on second commercial, clinical microscope, will be briefly exchanged with the primary scope to take additional images of the surgical field.
Study Duration	12-18 months
Study Center(s)	Single-center, Dartmouth-Hitchcock Medical Center
Objectives	The primary study objective is to determine if microdoses of ABY-029 (up to 6X) lead to detectable signals (defined as signal-to-noise ratio, SNR ≥ 10 , with wide-field iFI) in sampled tissues with an EGFR pathology score ≥ 1 based on histological staining. The secondary study objective is to assess diagnostic accuracy of ABY-029 detection by iFI and intraoperative probe relative to histopathology diagnosis, and other indicators (e.g. proliferation, infiltration, etc.) as the gold standard, and to measure the molecular uptake and concentration of ABY-029 in resected specimens.
Number of Subjects	A minimum of 6 and a maximum of 12 adult patients with a diagnosis of recurrent glioma will be enrolled.
Diagnosis and Main Inclusion Criteria	Operable brain tumor in adults with pre-surgical diagnosis of recurrent glioma.

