Study Product, Dose, Route, Regimen	
Criteria for successful iFI are locations of all EGFR positive samples (defined as having a pathology score ≥ 1 based on histological staining) having a measurable signal (defined as SNR ≥ 10). A single microdose of ABY-029 at 30 nanomoles (237μg) will be injected into the first 3 patients. If samples from these subjects meet successful iFI criteria, 3 more patients will be enrolled at the same dose, concluding the study with a total of 6 subjects. Otherwise, the ABY-029 dose in the next 3 patients will be increased to 3X (90 nanomoles, 711 μg). If samples from these subjects meet successful iFI criteria, 3 more patients will be enrolled at the 3X dose, concluding the study with a total of 9 subjects. If iFI criteria are not met, the next 3 patients will be enrolled at 6X dose (180 nanomoles, 1.42 mg). If iFI criteria are met, 3 more patients will be enrolled the 6X dose, concluding the study with a total of 12 subjects. If iFI criteria are not met in the first 3 patients at the 6X dose, enrollment will be stopped with a total of 9 subjects.
 
Because of the microdosing levels used, the results of the Dartmouth Toxicity Study (at 10X, 100X, 1000X doses), and the safety profile of similar compounds (e.g. ABY-025), we do not anticipate any serious adverse events (SAEs) related to ABY-029.

Duration of administration	ABY-029 will be administered by IV injection on day of surgery, approximately 1-3 hours prior to the procedure.
Reference methods	Post-operative histopathology will serve as the gold standard.
Statistical Considerations	Repeated measures analyses of variance will be performed to account for multiple samples from each patient. Student's t-test will be used to evaluate ABY-029 fluorescence signal detection in tumor relative to normal brain with iFI and intraoperative probe. Empirical ROC curves and logistic regression analysis for clustered binary data will be used to evaluate the accuracy of ABY-029-specific fluorescence in discriminating between EGFR+ glioma tumor, EGFR- glioma tissue, and normal tissue when detected by iFI and/or intraoperative probe.

1 Introduction

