6.1 Surgical Visit

After the study drug is administered (~1-3 hours prior to surgery), the patient will be prepared and transported to surgery as per routine at Dartmouth-Hitchcock. In the OR, patient positioning, registration of the MR image-guidance system, preparation of the surgical field, and draping will follow standard practice, as will scalp incision and craniotomy. Upon opening of the dura, the coregistered and tracked Zeiss Pentero operating microscope adapted for intraoperative fluorescence imaging (iFI) at 800 nm will be brought in to begin conventional image-guided microsurgical technique for tumor resection. At approximately 4 time points during each surgery and/or at the discretion of the surgeon, data/image and specimen acquisitions will occur. Three (3) will typically occur at first exposure of tumor, at the approximate mid-point of tumor resection (when a significant tumor tissue is in the field), and at a point nearing but prior to completion of tumor resection (when small amount of tumor tissue remains), and a fourth may occur at presumed end of resection. At each time point, iFI acquisitions will be recorded. The surgeon will then focus the coregistered microscope at discrete points in the operative field which exhibit non-, weakly, moderately, and strongly fluorescent emissions, if evident on the iFI scan. At each point, a second iFI will be acquired, optical probe measurements will be recorded and a surgical biopsy specimen will be obtained (except at presumed end of resection when no more tissue is planned for excision). Since the 2nd iFI, probe data and biopsy sample will occur each time at the focal point of surgical microscope which is coregistered, all intraoperative images, data and specimens will also be coregistered. If no signal is evident on the iFI scan, the surgeon will sample several locations in the surgical field by focusing the operating microscope on points of interest intended for resection, performing the probe measurements and biopsying the positions for later analysis. iFI and optical probe readings will also be acquired from normal brain to establish baseline/background signal levels for the case. Additionally, an imaging module mounted on a second commercial, clinical microscope, will be used to acquire images during surgery. Acquiring these images will involve moving the primary clinical scope out of the field, positioning the new scope to acquire images, and moving the primary scope back into place. This process will take approximately three minutes or less and poses no additional risk to the patient. When the case is performed in the Center for Surgical Innovation, and when indicated clinically, iMR (intraoperative MRI) may be acquired and resection may continue based on the findings. In these cases, iFI, optical probe and biopsy may occur at locations planned for resection. We have used these same coregistered image, data, and biopsy procedures in our current studies of ALA-induced PpIX fluorescence and have collected high quality information from up to 12-16 surgical specimens per case (~10 on average).

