6.3 Specimen Analysis

Biopsy samples taken at the time of surgery for research purposes and processed for IHC will be scored by a pathologist according to the following criteria: 0 = no staining; 1 = low membranous staining around cells; 2 = medium membranous staining completely around cells; and 3 = high membranous staining completely around cells. Standard formalin-fixation with paraffin embedding will be used for histopathologic type and grade to confirm diagnosis of astrocytoma or glioblastoma (following WHO criteria) by the study neuropathologist. As these tumors are recurrences and patients have received radiation and chemotherapy, an assessment of reactive gliosis vs. residual/recurrent glioma will also be scored as well as tumor burden and necrosis using methods previously described. Here, histopathology will be classified as non-tumor tissue, solid tumor, infiltrating tumor, or indeterminate. Infiltrating tumor will be further graded into <33% tumor, >33% but <67% tumor, and >67% tumor). Proliferation will be assessed by quantitatively scoring Ki-67 immunopositive cells. ABY-029 binding to tumor cells in the specimen will be evaluated by performing IHC with secondary antibodies directed against the anti-EGFR Affibody following the protocol. EGFR protein expression often corresponds to gene amplification, thus, we will assess gene-protein correlations on a cell-by-cell basis by performing both IHC for EGFR protein and CISH for EGFR gene amplifications using a multi-spectral analysis microscope (Nuance) to distinguish in individual tumor cells. Frozen tissue will be solubilized and evaluated for quantitative fluorescence using fluorimetry. Western and/or ELISA will be used if the signal is not sufficiently strong.

7 Statistical Plan

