Secondary study objectives will be assessed by performing analyses on the iFI and probe data as a diagnostic test with the corresponding specimen histopathological diagnoses as the gold standard. Predictive models (for each pathology) of the odds of tumor positivity for biopsies given concentration of ABY-029 will be constructed. Histologically confirmed tumor status from biopsies will be treated as a binary outcome with a logit link function in a generalized linear mixed model (SAS GLIMMIX) with a subject-specific random effect to account for intra-individual correlations among biopsies. The iFI and/or probe fluorescence measures will be introduced first as linear terms. Interactions and polynomial fits will also be assessed via goodness of fit statistics. The predictive accuracy of the model fit will be summarized through a concordance index, i.e., area under the ROC curve formed with the fitted probabilities of tumor. Analyses will be repeated for other histopathological indicators (beyond tumor/non-tumor) such as degree of proliferation, infiltration, ABY-029 binding, among others.

7.3 *Subject Population(s) for Analysis*

This study will involve patients with recurrent intra-cranial malignant glioma judged to be operable. Subjects eligible for enrollment in the trial will be patients with a previously resected high grade glioma with tissue positive for EGFR expression (pathology score ≥ 1 based on histological staining).

8 Safety and Adverse Events

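### Section 7.2 does not say whether the AUC of the mixed-model fitted probabilities includes the patient effect; if it does, the AUC partly credits knowing which patient a biopsy came from.

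*Combined protocol and SAP*

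**What the plan says.** Diagnostic accuracy of iFI and the probe against histopathology is a secondary objective (Section 2). Section 7.2 gives the analysis. The outcome is set first: "Histologically confirmed tumor status from biopsies will be treated as a binary outcome with a logit link function". The model is a "generalized linear mixed model (SAS GLIMMIX) with a subject-specific random effect to account for intra-individual correlations among biopsies". Fluorescence enters as a linear term, and interactions and polynomials are then judged by goodness of fit. The only accuracy summary named in 7.2 is a concordance index, the "area under the ROC curve formed with the fitted probabilities of tumor". The section does not say whether the fitted probabilities use the predicted patient effect or the fixed effects alone. It describes no validation step, and for this model it does not say whether doses are pooled.

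The Study Summary (Statistical Considerations) is broader: "Empirical ROC curves and logistic regression analysis for clustered binary data will be used". Section 7.2 does not repeat the empirical curves or say which AUC will be reported.

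**The concern.** A predicted patient effect is learned from the same histology results that the AUC then tries to predict. Patients with more tumour-positive biopsies receive higher fitted probabilities whatever their fluorescence. An AUC built on those probabilities therefore mixes two things: how well the signal separates tumour from non-tumour, and how far patients differ in the share of their biopsies that are tumour. A surgeon imaging a new patient does not have the second piece of information.

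The reading of the secondary endpoint is at stake. Under one permitted reading of 7.2, a useless signal would be reported with an AUC clearly above 0.5, and a modest signal would look stronger than it is. Two analysts could report different values from the same data.

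**Working it through.** The plan states no AUC, target AUC or precision for this objective, so there is no figure of its own to reproduce. The check is on what the stated rule does.

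**Inputs from the documents.** 10 specimens per patient on average (7.1, 7.2). 3 to 6 patients at one dose (7.2). In total, "A minimum of 6 and a maximum of 12 adult patients with a diagnosis of recurrent glioma will be enrolled".

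**Assumptions (not in the documents).** Between-patient SD of the log-odds of tumour: 0, 0.5 or 1. Baseline odds of tumour: 1:1 and 2.7:1. Log-odds slope per SD of fluorescence: 0 (useless), 0.7 or 1.4.

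**Model.** logit P(tumour) = a + b·x + u, where x is the biopsy's signal and u the patient effect.

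**Step 1: fixed effects only.** a + b·x is monotone in x, so its AUC equals the raw-signal AUC A if the fitted b is positive, and 1 − A if it is negative. For a useless signal the mean is about 0.5 + SD(A)·√(2/π). The simulated SD(A) with 6 patients is 0.07 to 0.09:
- 0.5 + 0.07 × 0.798 = 0.556
- 0.5 + 0.09 × 0.798 = 0.572

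This matches the simulated 0.56-0.57. Once the signal is informative the sign is rarely wrong. At slope 0.7 the excess over the raw AUC is at most 0.001 with 6 to 12 patients and 0.007 with 3.

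**Step 2: patient effect included.** Take b = 0, with t_i tumour and n_i non-tumour biopsies in patient i. All biopsies of one patient then share one fitted probability, and

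AUC = Σ_i Σ_j t_i n_j [1(u_i > u_j) + ½·1(u_i = u_j)] / (Σt · Σn).

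The predicted u_i follow the observed tumour fractions, so this exceeds 0.5 whenever those fractions differ and the estimated patient variance is above zero. Fluorescence plays no part in it.

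**Step 3: size.** 500 simulated datasets per scenario, fitted by maximum likelihood with Gauss-Hermite quadrature and empirical Bayes patient effects. Columns 2 to 4 are mean AUCs for a useless signal with 6 patients × 10 biopsies. The last two columns are the excess of the AUC with the patient effect over the raw AUC. Their ranges cover 3 to 12 patients, except the 0.12, which is for 6.

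| Patient SD | With patient effect | Fixed effects only | Raw signal | Excess, slope 0.7 | Excess, slope 1.4 |
|---|---|---|---|---|---|
| 0 | 0.60-0.62 | 0.56-0.57 | 0.49-0.51 | 0.02-0.03 | 0.01 |
| 0.5 | 0.66 | 0.56-0.57 | 0.49-0.51 | 0.05-0.07 | 0.02-0.03 |
| 1 | 0.74-0.75 | 0.56-0.57 | 0.49-0.51 | 0.12 | 0.06-0.08 |

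The chance that a useless signal yields an AUC of 0.70 or more with 6 patients is 19-25% (SD 0) and 70-73% (SD 1) with the patient effect, 0-4% with fixed effects only, and 0-2% for the raw signal. More patients do not cure it: at SD 1 the null mean is 0.72, 0.74-0.75, 0.77 and 0.77-0.78 for 3, 6, 9 and 12 patients.

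**Step 4: the sampling scheme.** Section 6.1 samples "discrete points in the operative field which exhibit non-, weakly, moderately, and strongly fluorescent emissions, if evident on the iFI scan". Drawing each patient's biopsies from four fluorescence levels gives null means of 0.59-0.64 (SD 0) and 0.72-0.78 (SD 1), which is the same picture.

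**Step 5: is a raw AUC over all pairs of biopsies enough?** Not if whole patients are brighter or dimmer than others. With 6 patients, patient logit SD 1 and an assumed patient-level signal shift of SD 1:
- Signal useless within patients, shift correlated 0.6 with tumour fraction: all-pairs AUC 0.60, within-patient AUC 0.50.
- Slope 0.7, uncorrelated shift: all-pairs AUC 0.62, within-patient AUC 0.68-0.69.

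Pooling doses acts in a similar way. If signal scales with dose (assumed; log-signal SD 0.5-1), plain pooling of 9 to 12 patients lowers the AUC from 0.66-0.68 to 0.59-0.66 at slope 0.7.

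**The case against.** **The inflation depends on a choice the plan leaves open.** This stands. A reader might infer that the planned AUC is inflated. The documents do not support that: 7.2 never says the patient effect is included, and an analyst who used fixed effects only would report essentially the raw AUC for an informative signal. The fault is a missing specification.

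**The protocol already plans an accuracy measure free of the patient effect.** This also stands in part. A reader of 7.2 alone might infer that no such measure exists, but the Study Summary names empirical ROC curves and 7.2 does not withdraw them. What is missing is their place in the detailed plan and a statement of which AUC is reported.

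**The largest figures come from the unfavourable end of the range.** True. They need a useless signal and a patient SD of 1. At SD 0 to 0.5 with an informative signal the excess is 0.01-0.07, at or below the sampling SD of the raw AUC with 6 patients (0.07-0.09). Sampling error is random, however, whereas this excess always runs upwards on average.

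**The reference standards might seem to conflict.** The Study Summary speaks of "discriminating between EGFR+ glioma tumor, EGFR- glioma tissue, and normal tissue when detected by iFI and/or intraoperative probe", while 7.2 uses tumour status, and in Section 6.3 "histopathology will be classified as non-tumor tissue, solid tumor, infiltrating tumor, or indeterminate". A reader might call this a contradiction. But 7.2 plans a model for each pathology and repeats the analyses for other indicators, so it is missing detail at most and not part of this point.

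**Stakes are modest.** Agreed. A reader might fear that dose choice is affected. It is not: escalation and stopping follow the iFI signal-to-noise criterion (Section 1.5), not this index.

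**Conclusion.** The point holds as an ambiguity with a material consequence under one of its two readings. That 7.2 leaves the choice open, and that including the patient effect rewards patient identity, follows from the text and the algebra. The size rests on assumed between-patient SDs of 0 to 1, for which the documents give no value. With 6 patients, a useless signal would show a mean AUC of about 0.60-0.62, 0.66 or 0.74-0.75, against about 0.50 for the raw signal. At a slope of 0.7 the excess is about 0.02-0.03, 0.05-0.07 or 0.12. With fixed effects only and a linear term the problem is negligible for an informative signal. Polynomial and interaction terms were not simulated. It should be settled before the analysis; it affects how a secondary endpoint is reported, not how the trial is run.

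**What to change.** In Section 7.2:

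1. Carry forward the empirical ROC from the Study Summary. Make the accuracy measure the empirical AUC of the raw iFI signal, and separately of the raw probe signal, with direction fixed in advance (higher means tumour) and a patient-clustered confidence interval.
2. Report beside it a within-patient AUC that counts only pairs of biopsies from the same patient. This removes patient-level signal shifts and dose differences. Patients whose biopsies are all of one class contribute no pairs, so give the number of contributing patients.
3. If doses are pooled in the all-pairs AUC, count only pairs taken at the same dose.
4. Keep the mixed model for the odds of tumour. Label any model-based AUC, such as one combining iFI and probe, as supportive, in-sample and from fixed-effects-only predictions.

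The cost is a few sentences and a few lines of code, with no change to conduct or data collection. The reported AUC will probably be lower than one that includes the patient effect, and its interval will be wide. The half-width is about 0.14-0.17 with 6 patients (1.96 times a simulated SD that rounds to 0.07-0.09), and wider if patient-level signal shifts exist.

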3.3 Secondary Study Endpoints

Secondary endpoints of the study are diagnostic accuracy of ABY-029 detection by iFI and intraoperative probe relative to histopathology tissue diagnosis, and other indicators (e.g. proliferation, infiltration, etc.) as the gold standard, and measurement of molecular uptake and concentration of ABY-029 in resected specimens.

4 Subject Selection and Withdrawal

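### Section 7.2 repeats a yes/no accuracy model for graded indicators without a scale or cut-point, and includes ABY-029 binding, which is not independent of ABY-029 fluorescence

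*Combined protocol and SAP*

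**What the plan says.** Section 3.3 makes diagnostic accuracy a secondary endpoint, judged against tissue diagnosis and "other indicators (e.g. proliferation, infiltration, etc.) as the gold standard".

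Section 7.2 gives one model for this. Models "of the odds of tumor positivity for biopsies given concentration of ABY-029 will be constructed", with iFI or probe fluorescence as the predictor. Confirmed tumor status "will be treated as a binary outcome with a logit link function in a generalized linear mixed model (SAS GLIMMIX"), with a random effect for subject. Accuracy is summarised by the "area under the ROC curve formed with the fitted probabilities of tumor". The paragraph ends with an open-ended extension: "Analyses will be repeated for other histopathological indicators (beyond tumor/non-tumor) such as degree of proliferation, infiltration, ABY-029 binding, among others". The statistical entry in the Study Summary likewise names ROC curves and logistic regression for clustered binary outcomes.

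Section 6.3 says how the extra indicators are recorded:

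- Proliferation: "Proliferation will be assessed by quantitatively scoring Ki-67 immunopositive cells".
- Infiltration: "Infiltrating tumor will be further graded into <33% tumor, >33% but <67% tumor, and >67% tumor". These bands sit within a four-way classification that also has non-tumor, solid and indeterminate classes.
- ABY-029 binding: "performing IHC with secondary antibodies directed against the anti-EGFR Affibody". No grading scale or positivity threshold is given for it.

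**The concern.** The only model in the secondary plan takes a two-class outcome, and so does its AUC. It is to be repeated for a quantitative score, an ordered grade and a stain for the injected agent. Nothing states the outcome scale, link, cut-point or collapsing rule for any of these.

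Two things follow. First, if the repeat is literal, someone must choose what counts as positive, possibly after seeing the data. That loses information in a study with 3 to 6 patients per dose, and it leaves room to pick the most favourable split. Second, a high AUC against ABY-029 binding could be reported beside the tumor AUC as though it were further evidence of diagnostic accuracy. Both sides of that comparison depend on how much of the same agent reached the tissue.

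**Working it through.** **Inputs from the documents.** Model, accuracy summary and list of indicators: section 7.2. Scales: section 6.3. Specimens: 30 from 3 patients at one dose and up to 60 from 6, at an average of 10 per patient (section 7.2). The plan gives no sample size, power or cut-point for these analyses, so there is no stated figure to reproduce. The numbers below are illustrations, and their assumptions are mine.

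**1. Method against scale.**

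| Indicator | Recorded as (6.3) | What a literal repeat of 7.2 needs |
|---|---|---|
| Ki-67 | quantitative score | a cut-point; none given |
| Infiltration | three ordered bands, plus non-tumor and solid | which boundary is positive (five classes, so at most 5 - 1 = 4 choices); none named |
| ABY-029 binding | staining for the Affibody peptide | a cut-point; none given |

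The indeterminate class has no stated handling either.

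**2. Information kept after a cut.** For a normal score cut at quantile q, relative efficiency is φ(z_q)² / [q(1 - q)].

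- Median: 0.3989² / 0.25 = 0.637, a loss of about 36%.
- 33/67 split: 0.593.
- 20/80 split: 0.490.
- 10/90 split: 0.342.

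**3. What that means for power.** Assume a correlation of 0.5 between fluorescence and score, two-sided 0.05, and a Fisher-z test: power = Φ(atanh(r)·√(n - 3) - 1.96). A median cut shrinks r to 0.5 × √0.637 = 0.399.

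| Specimens | Score kept | Median cut |
|---|---|---|
| 30, independent | 0.81 | 0.59 |
| 60, independent | 0.99 | 0.89 |
| 30, ICC 0.2: 30 / (1 + 9 × 0.2) = 10.7 effective | 0.33 | 0.22 |
| 60, ICC 0.2: 60 / 2.8 = 21.4 effective | 0.66 | 0.44 |

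The ICC is assumed. This design effect is a rough allowance and is pessimistic where fluorescence varies within a patient.

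**4. The AUC depends on the cut.** With the same correlation of 0.5 (400,000 simulated pairs), AUC is 0.73 at a median cut and 0.77 at a 10% or 90% cut. An AUC against Ki-67 is not one defined quantity until the cut is fixed.

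**5. Choosing the cut from the data.** With fluorescence and score unrelated (2,500 simulated data sets per setting, independent specimens, two-sample t-test at 0.05, smallest p-value kept):

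- Three candidate cuts (33%, 50%, 67%): false-positive rate 0.123 with 30 specimens and 0.115 with 60.
- Nine cuts (10% to 90%): 0.256 and 0.264.

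**6. Binding as a reference.** Let A be local uptake of the agent, with fluorescence F = A + error and binding stain B = A + separate error. The error variance is 1/reliability - 1. Let tumor status be unrelated to A, with an assumed 60% of specimens positive.

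| Assumed reliability | AUC of F against tumor | AUC of F against median-cut B |
|---|---|---|
| 0.5 | 0.50 | 0.73 |
| 0.7 | 0.50 | 0.83 |
| 0.9 | 0.50 | 0.94 |

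An agent that carries no information about tumor would still score well against its own binding stain. This does not depend on the cut-point problem in steps 2 to 5.

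**The case against.** The plan never says that these scores will be dichotomised. Section 7.2 ties the binary outcome to tumor status alone, and its wording for proliferation speaks of degree. The named procedure, GLIMMIX, also fits ordinal and continuous outcomes. A reader might infer that the data must be cut at arbitrary points. The documents do not support that: the cut is needed only if the repeat is literal, and for infiltration the possible boundaries are fixed in advance by section 6.3. What stands is that the literal reading is the only one with a described method, and the Study Summary's reference to binary data supports it.

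A reader might also infer that the dye is being checked against itself. That is not exact. The optical signal comes from IRDye 800CW and the stain is directed at the Affibody peptide, so these are different measurements of one agent. Comparing them is a legitimate check of localisation and fits the uptake objective in section 2. Nor does section 3.3 name binding among its reference standards, except possibly under its open-ended wording. What stands is that section 7.2 lists binding in the paragraph that treats fluorescence as a diagnostic test, and that the two measurements are not independent.

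Finally, the efficiency figures assume a normal score and independent specimens. They do not apply to infiltration, which is already banded, or to the binding point. The 20/80 and 10/90 splits appear nowhere in the documents, so converting the percentages into a number of lost specimens would not be an estimate for this trial.

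**Conclusion.** The point holds as a cheap improvement. Section 7.2 leaves scale, link and cut-points unstated for indicators that section 6.3 records on finer scales, and the one method it describes would need a cut. At a median split of a normal score the cost is about 36% of the information. That figure is illustrative and assumes independent specimens; clustering lowers absolute power further under either analysis. If the cut were picked from the data, a nominal 5% error rate could become about 12% with three candidates and about 26% with nine, under the assumptions shown.

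An AUC against ABY-029 binding is not evidence of accuracy for tumor. The 0.73 to 0.94 range rests on assumed reliabilities of 0.5 to 0.9, but the lack of independence follows from section 6.3 alone.

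The effect is confined to secondary analyses in a pilot of 6 to 12 patients. The SNR endpoint and the dose-step rule are untouched.

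**What to change.** In section 7.2, replace the sentence that repeats the analyses with four statements:

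- **Ki-67:** analyse on its quantitative scale with a patient-clustered mixed or rank-based model. If transformed, use a transformation that allows zeros; a plain logarithm fails for specimens with no positive cells.
- **Infiltration:** analyse as one ordered outcome built from the section 6.3 classes, with a patient effect. Confirm with the study neuropathologist how solid tumor ranks against the highest infiltration band, since the plan does not say. Set indeterminate specimens aside in the main analysis, with a sensitivity analysis that includes them. State in advance the rule for merging sparse adjacent bands.
- **Accuracy measure:** for both, report a concordance index suited to an ordered or continuous outcome. This keeps the accuracy endpoint of section 3.3 without a data-chosen cut.
- **ABY-029 binding:** report its association with fluorescence under the uptake objective, as target engagement, and remove it from the diagnostic accuracy analyses.

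Section 7.2 already uses ANOVA by EGFR score and rank correlation for the primary objective, so keeping the full scale is in line with the rest of the plan.

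The cost is wording only, with no new data or assays. The ordered model assumes a common odds ratio across classes and may be unstable with 3 to 6 patients per dose, which is why the merging rule should be set beforehand.
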